
## **D Study Design**

### **D1 Overview or Design Summary**

At each of the participating campuses, we will recruit students from the undergraduate population. Some campuses may decide to provide us with a random sample (requesting from the Registrar [or equivalent campus unit] which is oversampled by gender, race/ethnicity, and socioeconomic status [e.g., Pell grant recipients] to ensure that participant samples are diverse and representative on these dimensions).

Students will be recruited via emails to their campus email address to participate in the screen.

---

Students will be asked at the start of the screen if they would like to opt out of receiving information about potential future studies. We will create an entire new registry of students from those who **do not select to opt out** of future studies, ensuring we will not be able to contact those who opted out of future contact from the new registry.

Following the screen students will receive personalized feedback about their results. The personalized feedback will be automated through Qualtrics, allowing for an efficient yet individualized feedback approach. The personalized feedback will include either an end of survey message thanking the individual for their participation (and a referral for treatment if applicable) or an invitation to participate in the full study as follows:

1. No symptoms or low risk for depression, anxiety, and EDs - they will not be eligible to participate in the next phase of the study.
2. Low risk with trauma, insomnia, or substance abuse - receive referral for clinical evaluation and intervention.
3. At high risk for or with clinical anxiety, depression, or an ED not currently in treatment; own a smartphone - will be invited to participate in phase 2 of the study.
4. At high risk for or with clinical anxiety, depression, or an ED currently in treatment and/or without a smartphone - will be encouraged to continue in treatment provided with a referral for clinical evaluation and intervention.
5. Anorexia nervosa - receive referral for clinical evaluation and intervention.

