All students who receive a recruitment email will be automatically entered into a sweepstakes for one of 40 \$100 electronic gift card prizes.

In order to assess mental health treatment utilization, in addition to assessing this via self-report, we will obtain aggregate counts of participants in therapy from campus counseling/health centers, by random assignment group at baseline, 6 months, and 2 years. To assess academic outcomes, including term by-term GPA and enrollment status (to assess drop-out), at the end of the 2 years we will obtain aggregate data of participants from Registrars by semester/term to include GPA and attrition rate by condition.

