## **2.a Inclusion Criteria**

Screening survey inclusion criteria: Undergraduate students at participating colleges and universities who are 18 years old and older.

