## **2.h Data Collection and Follow-up for Withdrawn Subjects**

When a participant withdraws from the study, the research team will stop collecting data from them.

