## ***F3 Analysis Plan***

To evaluate efficacy of the mHealth platform vs. usual care, in engaging participants (Aim 1) we will use hierarchical logistic regression to examine uptake (i.e., individuals beginning any sort of treatment). Outcome will be at least one session of mental health services use (either online or in-person) assessed at 6 weeks, 6 months, and 2 years. Using hierarchical logistic regression, we will also examine efficacy in reducing or preventing number of students with mental health disorders (i.e., a positive screen for at least one of anxiety, depression, or ED as the outcome reflecting a "clinical case") assessed at 6 weeks, 6 months and 2 years, with a primary endpoint of 2 years. This allows for a single, universal outcome applicable to everyone in the study. Both logistic regression models will include random intercepts for colleges and for students nested within colleges, and account for repeated assessments within students, and will estimate the following fixed effects: main effect of time (coded as a factor variable, including baseline, 6-weeks, 6-months, and 2 years), treatment condition, and two-way interaction between time and treatment condition.

To evaluate reduction in disorder-specific symptoms (Aim 2b) and improvement in quality of life (Aim 2c), multilevel models will be used. Analyses of symptom change will be conducted within each clinical disorder subgroup separately with relevant symptoms as the response variables. We will also use a z-score to standardize primary symptom measures to obtain an estimate for a unified intervention effect. All symptom models will include random intercepts for colleges and for students nested within colleges, account for repeated assessments within students, and will estimate the following fixed effects: main effect of time, treatment condition, and two-way interaction between time and treatment condition. Parameter estimates from these models will allow separately

---

comparing change between arms from pre to 6 weeks, pre to 6 months, and from pre to 2-year follow-up. Each model will use dummy-coded factor terms as a stringent test of the treatment to ensure that: 1) treatment was associated with significantly greater change from pre to post than the control group; and 2) gains made in treatment at 6 weeks are maintained and significantly greater than baseline at each follow-up.

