
Analyses for Aim 4: Economic evaluation analyses (Aim 4a) were designed to provide information for stakeholders considering implementing the mobile platform^217. As such, analyses will be conducted from the payer's perspective to reflect opportunity cost for the payer. We will use TreeAge software, taking a multistep approach. Overall, the model will be evidence-based and fully validated using study data. A decision analytic

---

model using a microsimulation approach will be used to provide the most flexibility for testing model assumptions and provide clear evidence to decision-makers concerning reliability of results. Internal validation of the model will be conducted by comparing outcomes of participants whose data were used to construct the model to their predicted outcomes. Model fit will be tested using the R^2 statistic for continuous data and the chi-squared statistic for categorical data. External validity will be tested by comparing the model's predicted outcome to actual for participants who were "excluded" from the model-building process. The outcome of interest is the net benefit of the intervention compared to usual care at 2 years. Sensitivity of the decision model to the assumptions, including time frame, discount rate, and perspective, will be thoroughly tested using deterministic and probabilistic sensitivity analyses. We will also calculate incremental cost-effectiveness ratios, corresponding to the incremental difference (intervention vs. control) in costs divided by the incremental difference in the primary outcome, the number of clinical cases at 2-year follow-up. Monte Carlo simulations and cost-effectiveness acceptability curves will be used to present uncertainty around this estimate. Academic outcomes (Aim 4b) will be analyzed using the methods described for the primary outcomes under Aim 1. Academic outcomes will also be included into cost analyses, by translating drop-outs from college into losses in tuition (for institutions) and losses in lifetime expected productivity. Stakeholder attitudes (Aim 4c) will be assessed for variation using descriptive statistics, and will be used to predict intention to adopt the platform using ordered probit regressions (with Likert categorical variables corresponding to intention to adopt).

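### Aim 4b is assigned a student-level logistic model, but the plan obtains academic data only as registrar aggregates, and the attrition rate has no stated base or rule for graduates

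*Combined protocol and SAP*

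**What the plan says.** F3 Analysis Plan, under Aim 4: "Academic outcomes (Aim 4b) will be analyzed using the methods described for the primary outcomes under Aim 1". The Aim 1 method in the same section is hierarchical logistic regression: "Both logistic regression models will include random intercepts for colleges and for students nested within colleges". It also accounts for repeated assessments within students and codes time as baseline, 6 weeks, 6 months and 2 years.

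D1 Overview or Design Summary names the academic outcomes as "term by-term GPA and enrollment status (to assess drop-out") and gives the source, to be collected once follow-up is complete: "we will obtain aggregate data of participants from Registrars by semester/term to include GPA and attrition rate by condition".

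E2 Schedule of Measurements lists academic impairment, obtained from colleges, at baseline, 6 months and 2 years. F4 applies intent-to-treat with full-information maximum likelihood to every analysis. F3 also feeds college drop-out into the cost analysis as lost tuition and lost lifetime productivity.

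On who may be in the data, D1 says "we will recruit students from the undergraduate population" and section 2.a admits "Undergraduate students at participating colleges and universities who are 18 years old and older". Neither sets a class-year limit.

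**The concern.** The model named for Aim 4b and the data described for it are at different levels. The model needs one record per student per time point; the data are summaries by term and arm. The analysis as written therefore cannot be run, and a substitute would have to be chosen after the registrars report.

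The meaning of attrition is also left open. The documents do not state the denominator of the rate, or how a student who graduates, transfers or takes leave within 2 years is classified. Different colleges could supply different quantities, and the same figure enters the cost analysis. There an error in the level of drop-out is not removed by randomisation.

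**Working it through.** The plan gives no sample size, rate, SD or power specific to Aim 4b, so there is no stated figure to reproduce. The check is mainly a match of model to data.

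**1. Model against data**

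| Feature | Aim 1 model (F3, F4) | Academic data (D1, E2) |
|---|---|---|
| Unit | Student within college, repeated | Aggregate by term and condition |
| Outcome type | Binary | GPA (continuous); attrition rate |
| Time | Baseline, 6 weeks, 6 months, 2 years | D1: every term, collected at the end; E2: baseline, 6 months, 2 years |
| Missing data | Full-information maximum likelihood, all analyses | No student records to which it could apply |

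No row matches fully. No section describes student-level academic records or their linkage to study IDs.

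**2. What the aggregates contain.** Inputs: 7,884 randomised (A1) and 20 colleges of about equal size (F1). Assumptions: 1:1 allocation, and reports split by college.
- Per arm: 7,884/2 = 3,942.
- Cells per term: 20 × 2 = 40.
- Students per cell: 7,884/40 = 197.

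**3. Why the student level cannot be recovered.** Assume a rate of 20% in each of two terms. The SE of the arm-by-time contrast is sqrt(4 × 0.20 × 0.80 × (1 − ρ)/3,942), where ρ is the within-student correlation:
- ρ = 0: 0.0127
- ρ = 0.5: 0.0090
- ρ = 0.9: 0.0040

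All three fit the same term rates. The aggregates do not determine ρ, so they do not determine this SE.

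**4. What remains feasible.** For GPA, take 20 within-college arm differences (19 df, t = 2.093), an assumed SD of 0.5 to 0.8, and no variation in effect between colleges. The 95% half-width is 2.093 × SD × sqrt(2/3,942) = 0.024 to 0.038. With half still enrolled (1,971 per arm) it is 0.033 to 0.053. Variation in effect between colleges would widen these.

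**5. Graduates, if counted as attrition.** Let g be the share in class years that finish within 2 years. Let k be the arm difference in drop-out in those years relative to the other years. Everyone in the finishing years ends up not enrolled, whether by leaving or by graduating. The arm difference is therefore multiplied by (1 − g)/(1 − g + kg):

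| | k = 1 | k = 0.5 | k = 0 |
|---|---|---|---|
| g = 0.25 | 0.75 | 0.86 | 1 |
| g = 0.50 | 0.50 | 0.67 | 1 |

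Even with no dilution (k = 0), noise rises. Assume drop-out of 8% against 10% of all randomised, 3,942 per arm. Power is 0.87 with graduates counted as retained. Adding g = 0.25 to 0.50 to both arms gives 33% against 35%, up to 58% against 60%, and power of 0.43 to 0.47. All of g, k and the drop-out rates are assumptions.

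**The case against.** Four points can be made for the plan.

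- **Drop-out is planned for.** D1 names enrolment status and an attrition rate, and its list of registrar items is not worded as exhaustive. The team knows how many were randomised per college and arm, so a rate on that base yields a count. This stands. What is missing is a stated base and definition, not the outcome.
- **A linear model is already in F3.** That is so for the symptom outcomes, but Aim 4b does not cite it. It also has a student level ("All symptom models will include random intercepts for colleges and for students nested within colleges"), so it would repair GPA only if student records existed.
- **The E2 row may point to participant-level data.** It sits under the participant heading and is marked as obtained from colleges. It is ambiguous, but it does not override the explicit description of aggregates in D1.
- **Drop-out does not ordinarily mean graduation.** A reader might infer that attrition will be reported several times too high. The documents do not support this: no section counts graduates as drop-outs, and the class-year mix and drop-out rates are not given. The loss in step 5 is conditional on that reading.

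A reader might also take section 2.h, "When a participant withdraws from the study, the research team will stop collecting data from them", to mean that withdrawn students disappear from the registrar data. It speaks of data from the participant, whereas registrar totals come from the college. The question is open, and no effect is shown.

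**Conclusion.** The contradiction between F3 and D1 holds and needs no outside assumption: the Aim 4b model cannot be fitted at the student level to the data described, and its logistic form does not suit GPA. The time points also need reconciling. A college-level analysis of the aggregates is possible, so the data are usable; the specified analysis is not.

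The attrition definition is a secondary point. Its direction is clear if graduates are counted: a higher rate, a smaller or noisier arm difference, and a distorted cost input. Its size is not known from the documents and is zero if graduates are excluded.

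Aim 4b is a stakeholder outcome. Aims 1 and 2a to 2c are not touched, and the cost-effectiveness ratio still has clinical cases as its denominator. This should be fixed before the registrars are asked for data, but it does not threaten the trial's main conclusions.

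**What to change.** Reconcile D1, E2 and F3 in one of two ways.

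**(a) Keep aggregates.**
- Ask each registrar, by college and arm, for the number with a GPA, the mean and the SD in each term.
- Ask also for counts, with all randomised students as the base: graduated; transferred or on leave, where known; otherwise left. Transfers are kept apart because they may cost the institution tuition without the productivity loss.
- Analyse GPA by a linear analysis of within-college arm differences.
- Analyse drop-out by a college-stratified or grouped binomial analysis, with graduates not counted as drop-outs.
- Have the study team, not the registrar, identify withdrawn participants and state whether they stay in the list sent to registrars.

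**(b) Obtain de-identified student-level term records**, if consent and college agreements allow; these documents do not show whether they do. Then use the linear multilevel model already in F3 for GPA and a logistic model for drop-out.

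Under either option, name the term that gives the main result and say which terms stand for the scheduled time points.

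Cost of (a): rewording in D1 and F3, a slightly fuller registrar request, less precision than student-level data, and possibly small cells. Cost of (b): consent scope, college agreements and data-protection work, which cannot be judged from these documents.

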#### ***F4 Missing Outcome Data***

All analyses will be intent-to-treat analyses, using full-information maximum likelihood to handle missing data.

### **G Data Handling and Record Keeping**

#### ***G1 Confidentiality and Security***

All surveys will be completed on the secured survey platform Qualtrics. Survey data will be directly downloaded by our Screening Implementation and Data Coordinating site, UM, onto a protected server.

The data coordinating center will store the study data on secure, password-protected servers, with identifying information always kept separate from other study data (such as assessment responses). The data will only be accessible at any given time to the small number of study team members who need to use the data at that time. Data will be stored separately by participating institution until de-identified analytic files are assembled after data collection.

Data will be transmitted between sites using the secured file share program Box.

In order for the Fidelity Monitoring site, PSU, to review coach messages and data, SilverCloud Health will send PSU the data using Box. The data will be stored on password protected computers.

---

SilverCloud Health's privacy is aligned with US personal data protection principles and is HIPAA compliant.

All of our surveys will be completed using Qualtrics. Within Qualtrics we will create a contact list based on the registrar office database sent by the universities, which will allow Qualtrics to send out personalized email invitation to students. Only our Data Coordinating Center, the University of Michigan, will have access to the identifying information and will create an anonymous study ID for each participant who agrees to participate in the study. With the assistance of SilverCloud we were able to create a code to automatically link the anonymous Qualtrics Response ID from the survey with the self-selected username in SilverCloud. SilverCloud will only have access to limited data from Qualtrics for people who were randomized into the SilverCloud program. The data they will receive will help inform the coach on how to best support participants such as disorder risk level, suicide risk, gender, school, and co-morbidities. SilverCloud will also receive the email address of the participants in order to send them an automatic email to sign-up for the program."

## ***G2 Training***

All staff personnel are trained and comply with HIPAA regulations. All study team members will complete the CITI training and Good Clinical Practice training.

## ***G3 Performance Monitoring***

The Data and Safety Monitoring Plan for this trial includes close monitoring by the principal investigators (PIs) and four independent safety officers through the DSMB.

# **H Study Monitoring, Auditing, and Inspecting**

## ***H1 Study Monitoring Plan***

### **Data Safety and Monitoring Board (DSMB)**

An independent panel of experts with experience in clinical trials, health services research, biostatistics, and college mental health, consisting of four members who are not affiliated with the study – including an intervention researcher, a counseling center director, a biostatistician, and a patient advocate – will be appointed to constitute a Data Safety and Monitoring Board (DSMB). Members will be named prior to the commencement of the study. In addition, the study PIs (Drs. [name], [name], [name], and [name]) and designated staff will attend the DSMB meetings (as non-voting participants) and will be responsible for preparing and presenting data reports from the study. The DSMB will provide oversight and ongoing monitoring of participant safety, quality of data collection, and integrity of the study on a yearly basis. The DSMB will receive a report from the study Screening Implementation and Data Coordinating Center approximately four weeks before each review date. These reports will include the major variables necessary for monitoring safety, quality of data collection, and integrity of the study and will include otherwise blinded outcome data. The DSMB will prepare a report after every meeting based on the material received from the Screening

---

Implementation and Data Coordinating Center, which will be forwarded to the PIs to review at Study Executive Committee meetings and also forwarded to the IRB of Record by [name].

The DSMB will provide the following functions:

- Review of data (including masked data) over the course of the trial relating to efficacy, recruitment, randomization, adherence, retention, operating procedures, forms completion, intervention effects, ethnic/racial minority inclusion, and participant safety.
- Identification of problems relating to safety over the course of the study. Study PIs and Program Administrators will be informed by phone and via written report of their findings and recommendations.
- Identification of needs for additional data relevant to safety issues and request of these data from the study investigators.
- Selection of appropriate analyses and periodic review of data on safety and outcomes.
- Recommendations regarding recruitment, treatment effects, adherence, retention, safety issues, and continuation of the study.
- Provision of written reports to the Project Officer and the PIs following each DSMB meeting. These reports will summarize the key issues reviewed by the DSMB.

The frequency and type of data review is summarized in the following table, with additional information following:

Data	Review Frequency
Participant accrual (with demographic data)	Semiannually
Adverse events	Within 72 hours
Adverse and other events review	Annually
Intervention compliance	Annually
Discontinuation rules report regarding statistical power implications of drop-outs and missing data	Annually

## **I2 Funding Source and Conflicts of Interest**

This study is funded by NIH. Any potential financial conflicts of interest for individual research team members are reported according to the site-specific IRB requirements and procedures.

## **I4 Subject Stipends or Payments**

All students who receive a recruitment email will be automatically entered into a sweepstakes for one of 40 \$100 electronic gift card prizes.

---

Participating universities and colleges will have the option to offer their own incentives to their students. The incentives offered by the school will be reviewed by the research team to make sure they are compliant with the IRB regulations, i.e., not coercive.

Participants in the full study will be compensated by receiving an electronic gift card for completing the Baseline (\$5), 6 week (\$5), 6 month (\$10), and 2-year (\$20) follow-up assessments. Participants will be entered into a sweepstakes to win one of five \$50 gift cards after completing the Baseline, 6 week, 6 month, and 2-year surveys. In addition, once participants complete all four surveys, they will be entered into a sweepstakes to win one of ten \$100 gift cards.

## **15 Study Timetable**

The table below summarizes the timeline for the proposed five-year study. Each wave includes 5 campuses, for a total of 20 campuses across 4 waves. The waves are staggered by 6 months each, with the exception that the second wave will start a full year after the first wave to allow for careful adjustments in sampling (e.g., the size of the initial samples) if necessary. Data analysis and write-up will begin in month 43 so as to allow 18 months for these activities.

Study Timeline	Pre-award	1-6	7-12	13-18	19-24	25-30	31-36	37-42	43-48	49-54	55-60
Finalize procedures and protocol											
Finalize the study procedures	X	X									
Finalize assessment protocols	X	X									
Confirm and prepare study sites											
Step 1a. Confirm diverse set of 20 campuses		X	X								
Step 1b. IRB and institutional approvals		X									
Wave 1 campuses											
Baseline survey, 6-week follow-up, intervention				X							
6-month follow-up					X						
2-year follow-up							X				
Wave 2 campuses											
Baseline survey, 6-week follow-up, intervention					X						
6-month follow-up						X					
2-year follow-up								X			
Wave 3 campuses											
Baseline survey, 6-week follow-up, intervention						X					
6-month follow-up							X				
2-year follow-up								X			
Wave 4 campuses											
Baseline survey, 6-week follow-up, intervention							X				
6-month follow-up								X			
2-year follow-up									X		
Data analysis and write-up											
Preparation of de-identified data set for sharing									X	X	X

---

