All students in the usual care condition will receive a recommendation to seek care and will be given a list of resources available through their respective health or counseling center, including contact information to make an appointment and any other relevant resources on campus. Participants who will be completing the mobile interventions will be given a link to the program, hosted on a platform by our technology partners SilverCloud Health, and a program description. They will also be provided with instructions to download the SilverCloud Health program app, through which they can access the intervention, as well. Students are encouraged to log in to the intervention, create an anonymous username and password, and begin the program.

Both intervention and control groups will be asked to complete assessments at 6 weeks, 6 months, and 2 years after completing the baseline screen. 6 week assessments will ask participants to complete assessments of anxiety, depression, EDs, motivation for treatment, and mental health treatment utilization. The 6 month and 2-year follow-ups will include assessments of anxiety, depression, EDs, comorbidities, impairment/quality of life, motivation for treatment, mental health treatment utilization, and screening and treatment feedback. In addition, alternate contact information will be requested at baseline, 6, and 12 month follow-ups in order to maximize the likelihood that participants can be reached at the next follow-up assessment, including cell phone number for receiving SMS text-message reminders for follow-up surveys to be sent from the Qualtrics platform. Follow-up emails and SMS may also use images or other media to increase the students' attention and likelihood of response. In order to increase the response rate at 2-year follow-up the study team may call participants to remind them to complete the survey, the study team may leave a voicemail if the participant does not respond. All assessments will be conducted using Qualtrics survey platform.

Participants will be compensated by receiving an electronic gift card for completing the Baseline (\$5), 6 week (\$5), 6 month (\$10), and 2-year (\$20) follow-up assessments. Participants will be entered into a sweepstakes to win one of five \$50 gift cards after completing the Baseline, 6 week, 6 month, and 2-year surveys. In addition, once participants complete all four surveys, they will be entered into a sweepstakes to win one of ten \$100 gift cards.

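### Does starting analysis in month 43 leave too little time for the 2-year primary comparison once wave 4 is in?

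*Combined protocol and SAP*

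**What the plan says.** Section I5, Study Timetable, introduces its calendar with "The table below summarizes the timeline for the proposed five-year study". Four waves of 5 campuses make up the 20 campuses. On spacing it says "The waves are staggered by 6 months each, with the exception that the second wave will start a full year after the first wave", and on analysis "Data analysis and write-up will begin in month 43 so as to allow 18 months for these activities". The prose does not give the month in which wave 1 starts.

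Section D1 asks both arms to "complete assessments at 6 weeks, 6 months, and 2 years after completing the baseline screen". Section F3 takes the clinical-case outcome "with a primary endpoint of 2 years", and for the economic evaluation says "The outcome of interest is the net benefit of the intervention compared to usual care at 2 years". Section D1 also has registrar data on grades and attrition collected when the 2 years are over.

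Not everything waits for 2 years. The primary hypothesis in section A2 concerns uptake of services, which section F3 assesses at 6 weeks and 6 months as well as at 2 years.

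**The concern.** A reader who takes the 18 months as the allowance for the main analysis will find that the calendar cannot deliver it. The extra 6 months between waves 1 and 2 push wave 4 back, and a 2-year visit on top of that falls well after month 43. If the team had planned on 18 months with complete data, it would be short of time for the comparisons that matter most: clinical cases at 2 years, net benefit and cost per case. Under time pressure the 2-year comparison might be run before wave 4 had reported, leaving out the 2-year data of a quarter of the campuses (5 of 20).

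Two further points seemed to support this. Section G1 says "Data will be stored separately by participating institution until de-identified analytic files are assembled after data collection", which could mean that no analytic file exists in month 43. And the timetable, as it can be read here, puts wave 4's 2-year follow-up in months 43-48, too soon after its baseline in months 31-36.

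**Working it through.** **Inputs.** Study length of 60 months, wave stagger, and analysis start in month 43 (section I5); 2-year assessment at 24 months from the baseline screen (section D1). The start month of wave 1, S, is not given in the prose. Month 1 is the earliest possible; 7 and 13 are shown as assumptions.

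**The plan's own figure.** 60 − 43 + 1 = 18 months. It reproduces.

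**Wave starts.** S, S + 12, S + 18, S + 24.

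**Opening of the 2-year visit.** Add 24 months: S + 24, S + 36, S + 42, S + 48.

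**Months left from wave 4's opening to month 60.** max(0, 60 − (S + 48) + 1).

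| S | 2-year visit opens, waves 1 to 4 | Months left of the 18 |
|---|---|---|
| 1 | 25, 37, 43, 49 | 12 |
| 7 | 31, 43, 49, 55 | 6 |
| 13 | 37, 49, 55, 61 | 0 |

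The months left are upper bounds, because they count from the opening of the visit and not its close. Section D1 allows for late responders: "In order to increase the response rate at 2-year follow-up the study team may call participants to remind them to complete the survey". All 18 months would be available only if S + 48 ≤ 43, that is S ≤ −5, before the study begins.

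**What can be done earlier.** Wave 4's 6-month visit opens at S + 24 + 6 = S + 30: month 31, 37 or 43 for the three starts. So the 6-month visit has opened in every wave by month 43 at the latest, and the 6-week visit before that. Work on short-term uptake, 6-week targets and mediators, and the structure of the economic model does not depend on wave 4's 2-year data.

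**The table.** As extracted, the baselines of waves 1 to 4 sit in months 13-18, 19-24, 25-30 and 31-36, and their 2-year follow-ups in 31-36, 37-42, 37-42 and 43-48. From the first month of the baseline cell to the last month of the 2-year cell is at most 36 − 13 = 23 months (waves 1 and 2: 42 − 19 = 23) or 48 − 31 = 17 months (waves 3 and 4: 42 − 25 = 17), so no row holds a full 24 months. Wave 2 also sits one 6-month column after wave 1, where the prose has a year. Cells may have moved when the table was read from the PDF, so nothing here rests on it. Taken at face value, it shows wave 4's 2-year follow-up ending in month 48 and so leaves 60 − 48 = 12 months, the same figure as the bound for S = 1.

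**The case for a change.** The strongest case for a change is that the only analysis allowance in the protocol cannot apply in full to its 2-year endpoint, whatever the start month, and that the text does not say so. The bound needs only the prose. Months 1-6 of the table are given to finalising procedures and to approvals, so a start in month 1 is unlikely and the true margin is probably below 12 months. With a start in month 13, wave 4's 2-year visits would open after month 60. The correction would be a few sentences.

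The arithmetic in this stands; the inference does not. The sentence gives a period for analysis and write-up as a whole and reserves none of it for the 2-year comparison, so no stated time is wrong. No particular later start can be called likely: a start in month 7 fits the extracted baseline cells of waves 2 to 4, but it contradicts wave 1's own cell (13-18) and the extracted 2-year cells of waves 2 to 4. The sentence in section G1 is about keeping institutions' data apart. It gives no date and does not say that all 20 campuses must finish first.

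The fear of a premature comparison has no footing either. The model in section F3 takes baseline, 6 weeks, 6 months and 2 years together, and section F4 makes every analysis intention-to-treat. A run without wave 4's 2-year data would not be the specified analysis, and nothing in the timetable asks for one.

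**Conclusion.** The observation is right as a bound: at most 12 of the 18 months are available for the full-sample 2-year analyses, assuming the prose stagger, a visit 24 months after baseline, a 60-month study and a start no earlier than month 1. Assumed starts in months 7 and 13 leave 6 and 0.

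No change to the plan follows. This is an administrative calendar for a proposed study. The 2-year visit is fixed by each student's own baseline screen, not by a calendar month, so a slipped wave moves the date of the analysis and not the endpoint. The estimand, model, sample size and visits stay as they are, no bias is introduced, and restating the calendar would alter no result. If wave 1 started late, the consequence would be a shorter write-up or an extension, which is for the study's management to settle. The mismatch between table and prose is at most a clerical slip, and it cannot be judged from the extracted table.
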